13.5 Protocol amendments

Protocol changes may affect the legal and ethical status of the study and may also affect the statistical evaluations of sample size and the likelihood of the study fulfilling its primary objective.

Significant changes to the protocol will only be made as an amendment to the protocol and must be approved by UCB, the IRB/IEC, and the regulatory authorities (if required), prior to being implemented.

14 FINANCE, INSURANCE, AND PUBLICATION

Insurance coverage will be handled according to local requirements.

Finance, insurance, and publication rights are addressed in the Investigator and/or CRO agreements, as applicable.

16 APPENDIX

16.1 Protocol Amendment 1

Rationale

This nonsubstantial amendment is based on DMC recommendation, as a precaution additional safety monitoring has been added to the protocol. This precaution was not based on any related AE or reported symptoms. Additional vital sign measurements, specifically blood pressure, and criteria for further iv BRV dose allocation were added to further investigate blood pressure changes and ensure safety. Additionally, height measurements have been collected at various visits since the onset of the study, while these were inadvertently absent from the list of assessments. The protocol has therefore been aligned.

Specific changes

Section # and name	Description of change	Brief rationale
Study contact information	Updated Sponsor Study Physician, Clinical Project Manager, and Clinical Trial Biostatistician	Recent changes in study contacts
Section 5.2 Schedule of study assessments	Added definition of PCS Added cross reference to BP PCS values Table 10-6 Added text regarding additional safety monitoring and criteria for further iv and BRV dose allocation	Absent from previous version To clearly define BP PCS values To further investigate BP and ensure safety
Table 5-1 Schedule of Study Assessments (Screening Period through end of iv PK Period)	Added body height assessment	Added this text that was inadvertently omitted during protocol development
Table 5-2 Schedule for iv PK Period ECGs, vital signs, and PK sampling (15-min BRV infusion)	Added BP assessment along at 2hrs post infusion start and accompanying footnote Added description of when additional BP monitoring is required	To further investigate BP and ensure safety

Section # and name	Description of change	Brief rationale
Table 5-3 Schedule for iv PK Period ECGs, vital signs, and PK sampling (bolus [up to 2-min BRV infusion])	Added BP assessment along at 2hrs post infusion start and accompanying footnote Added description of when additional BP monitoring is required	To further investigate BP and ensure safety
Table 5-4 Schedule of study assessments for Down-Titration and Safety (BRV-free) Periods (subjects not continuing into the Long-Term, Open-Label Study)	Added body height assessment	Added this text that was inadvertently omitted during Protocol development
Section 8.1 Visit 1 (Day -10 to Day -1 for OLB, RxB, and IIB subjects; Day -20 to Day -11 for IOB subjects)	Added body height assessment	Added this text that was inadvertently omitted during Protocol development
Section 8.3 Visit 3 (Day 1) through Visit 12 (Day 6)	Added body height assessment Added a cross reference to BP PCS values Table 10-6	Added this text that was inadvertently omitted during Protocol development To clearly define BP PCS values
Section 8.6 Visit 13	Added body height assessment	Added this text that was inadvertently omitted during Protocol development
Section 10.3.2 Vital signs	Added text regarding additional safety monitoring Added Table 10-6 PCS abnormality criteria for the measurement of BP	To further investigate BP and ensure safety To describe the criteria for systolic and diastolic BP to be low or high PCS

---

## LIST OF ABBREVIATIONS

AE	adverse event
AED	antiepileptic drug
ALP	alkaline phosphatase
ALT	alanine aminotransferase
AST	aspartate aminotransferase
bid	twice daily
BMI	body mass index
BP	blood pressure
BRV	brivaracetam
CDISC	Clinical Data Interchange Standards Consortium
COVID-19	Coronavirus Disease 2019
CS	clinically significant
CSR	Clinical Study Report
C-SSRS	Columbia-Suicide Severity Rating Scale
CV	coefficient of variation
DBP	diastolic blood pressure
DOB	Date of birth
DMC	Data Monitoring Committee
ECG	electrocardiogram
eCRF	electronic case report form
ER	emergency room
h	hour
IIB	initiating iv BRV
Inf	infusion
IOB	initiating Oral BRV
IPD	Important protocol deviation
iv	intravenous
LOQ	limit of quantification
Max	maximum
MedDRA	Medical Dictionary for Regulatory Activities
Min	minimum
NCS	not clinically significant
OLB	open-label BRV
PCS	Possibly clinically significant
PCST	possibly clinically significant treatment-emergent
PDILI	Potential Drug Induced Liver Injury
PK	pharmacokinetics
PK-PPS	Pharmacokinetic Per Protocol Set
PQ/PR interval	time from the beginning of the P wave until the beginning of the QRS complex
PT	preferred term
PTAE	pre-treatment adverse event

---

QRS duration	duration of the combination of three of the graphical deflections seen on ECG
QT interval	time between the start of the Q wave and the end of the T wave in ECG
QTcB	QT interval corrected for heart rate (Bazett's formula)
QTcF	QT interval corrected for heart rate (Fridericia's formula)
RR	respiratory rate
RR-interval	time between successive Rs in ECG
RxB	Prescribed-BRV
SAE	serious adverse event
SAP	Statistical Analysis Plan
SBP	systolic blood pressure
SD	Standard deviation
SOC	system organ class
SS	Safety Set
SS-iv	Safety Set-iv
TC	Telephone contact
TEAE	treatment-emergent adverse event
ULN	upper limit of normal
VNS	Vagus Nerve Stimulation
WHODD	World Health Organization drug dictionary

REDACTED COPY  
This document cannot be used to support any marketing authorization application and any extensions or variations thereof.

## 1 INTRODUCTION

This Statistical Analysis Plan (SAP) defines the scope of statistical analyses and provides a detailed description of statistical methodology for the statistical analyses to support the final clinical study report for EP0065. This SAP is based upon the following documents: Final Protocol Amendment 1.0: 19 Jun 2019.

## 2 PROTOCOL SUMMARY

### 2.1 Study objectives

#### 2.1.1 Primary objectives

The primary objective of this study is to evaluate the pharmacokinetics (PK), safety, and tolerability of brivaracetam (BRV) administered as a 15-minute iv infusion and iv bolus (up to 2-minute infusion) in subjects  $\geq 1$  month to  $< 16$  years of age with epilepsy.

### 2.2 Study variables

#### 2.2.1 Pharmacokinetic variables

- Plasma concentration of BRV (parent compound only) before, during, and after iv BRV administration.

#### 2.2.2 Safety variables

##### 2.2.2.1 Primary safety variables

- Adverse events (AEs) throughout the study
- Subject withdrawals due to AEs

##### 2.2.2.2 Other safety variables

- 12-lead ECG values before, during, and after each iv BRV administration
- Blood pressure (BP), pulse rate, respiratory rate (RR), and temperature values before, during, and after each iv BRV administration
- Clinical laboratory parameters (hematology, chemistry, and endocrinology) pre and post treatment
- Urinalysis parameters pre and post treatment

Post treatment parameters will be only available for subjects who down titrate and perform Visit 13 assessments.

### 2.3 Study design and conduct

EP0065 is a Phase 2 multicenter, open-label study to evaluate the PK, safety, and tolerability of iv BRV administered as a 15-minute iv infusion and an iv bolus (up to 2-minute infusion) in subjects  $\geq 1$  month to  $< 16$  years of age with epilepsy.

Study medication is defined by iv infusion of BRV administered as a 15-minute iv infusion or an iv bolus (up to 2-minute infusion). Oral BRV can be administered during EP0065 but will not be considered as study medication for EP0065.

Approximately 50 enrolled subjects will receive iv BRV in the following age-based cohorts (approximately 12 subjects/cohort):

- Cohort 1:  $\geq 12$  to  $< 16$  years
- Cohort 2:  $\geq 6$  years to  $< 12$  years
- Cohort 3:  $\geq 2$  to  $< 6$  years
- Cohort 4:  $\geq 1$  month to  $< 2$  years

The age at Screening Visit will be the determining factor for age cohort assignment. Each age cohort will have approximately 50% of subjects with iv BRV infusion and 50% with bolus BRV.

The following subjects will be eligible for enrollment in EP0065:

- Open-label BRV (OLB) subjects: currently receiving oral BRV as participants in a long-term, open-label study
- Prescribed BRV (RxB) subjects: currently receiving prescribed oral BRV from commercial supply
- Initiating Oral BRV (IOB) subjects: not currently receiving BRV; first dose of BRV in EP0065 will be oral tablet or solution
- Initiating iv BRV (IIB) subjects: not currently receiving BRV; first dose of BRV in EP0065 will be by iv Infusion

For OLB and RxB subjects, the maximum BRV dose is 5mg/kg/day (rounded). For IOB and IIB subjects, the maximum BRV dose is 4mg/kg/day. Throughout the study, no subject may receive a dose greater than BRV 200mg/day. Subjects will receive oral BRV (tablets or oral solution) in equally divided doses; BRV oral solution may be given by enteric administration (eg, by feeding tube) based on subject need.

The EP0065 study periods and visits are described below. The PK assessments will be made during the iv PK Period only and safety data will be collected throughout the study, with intensive collection of safety data with each iv BRV dose administered. A Schedule of Study Assessments is provided in the protocol for the Screening through iv PK Periods and for the Down-Titration Period and Safety (BRV-free) Periods (for subjects not continuing BRV).

- Screening Period (1 to 10 days)

During the Screening Period, the OLB and RxB subjects will continue treatment with oral BRV using their assigned open-label study supply or prescribed commercial supply, respectively. The IOB and IIB subjects will not receive BRV during this period.

The OLB subjects will temporarily discontinue assessments in their long-term, open-label study when they enter EP0065. As such, all assessments for these subjects during the Screening Period (and subsequent periods of EP0065) will be recorded in the EP0065 Case Report form (CRF) until they return to a long-term, open-label study or discontinue BRV treatment.

- IOB Treatment Period (2 to 10 days of oral BRV treatment; for IOB subjects only)

Only IOB subjects who meet all eligibility criteria may participate in the IOB Treatment Period. No other subjects may participate in this period.

During the IOB Treatment Period, IOB subjects will initiate treatment with oral BRV 2mg/kg/day not to exceed 100mg/day for subjects with body weights  $\geq 50$ kg and must have, at minimum, 2 days of treatment with oral BRV before entry into the iv PK Period. Subjects who do not enter the iv PK Period will not be eligible for the long-term, open-label study.

The Investigator is permitted to adjust the oral BRV dose during the IOB Treatment Period in accordance with medical judgment (with a maximum dose of 4mg/kg/day, not to exceed 200mg/day for subjects with body weights  $\geq 50$ kg); however, subjects must have no change in the oral BRV dose for the 2 days prior to entry into the iv PK Period.

- iv PK Period (1 to 6 days, with Day 1 defined as the initial day of iv BRV infusion)

During the iv PK Period, iv BRV will be administered every 12 hours  $\pm 2$  hours (q12h  $\pm 2$ h). All subjects are to receive 1 to 2 consecutive doses of BRV; however, based on medical need, subjects may receive up to 10 consecutive doses of iv BRV. The PK sampling will occur with the first iv BRV administration and with 1 other iv BRV administration.

The first dose of iv BRV will be as follows:

- OLB, RxB, and IOB subjects: mg-to-mg equivalent of the oral BRV dose immediately prior to the iv PK Period; administered q12h  $\pm 2$ h after prior oral dose
- IIB subjects: 1mg/kg not to exceed a maximum of 50mg for subjects  $\geq 50$ kg

After subjects have completed PK sampling with 2 iv BRV infusions, the Investigator may adjust the BRV dose, but the adjusted dose must not exceed 5mg/kg/day (rounded) for OLB and RxB subjects and 4mg/kg/day for IOB and IIB subjects (with the maximums not to exceed 200mg/day). During the iv PK Period, BRV may only be administered intravenously. Enrollment will be sequential by descending age beginning with age-based Cohort 1. For each age cohort, the first half will receive the 15-minute infusion. The Data Monitoring Committee (DMC) will then meet to review safety and, as available, PK data. After the DMC safety review, the remaining half in that age cohort will receive iv BRV as a bolus (up to 2-minute infusion) and the next age cohort may begin the 15-minute infusion. Subjects may receive bolus infusions only after subjects in the preceding age cohort have completed bolus infusions and the DMC have reviewed these data. The DMC will meet no less than approximately every 6 months commensurate with enrollment.

Telephone contact (TC)-1 will occur 1 to 3 days after completing the final iv BRV dose in the iv PK Period to facilitate reporting of infusion-site related AEs.

- Down-Titration Period (up to 4 weeks) and Safety (BRV-free) Period (2 weeks)

Subjects who receive  $\geq 4$  doses of BRV during either the IOB Treatment Period or the iv PK Period and who do not plan to continue treatment with BRV or who discontinue from the study will enter a Down-Titration Period. Subjects who have received  $< 4$  doses of BRV may have BRV down titrated at the discretion of the Investigator. During the Down-Titration Period, subjects will have their BRV dose reduced by a maximum of half the dose every week for a maximum of 4 weeks until a dose of 1mg/kg/day (50mg/day for subjects with body weights  $\geq 50$ kg) is reached. Subjects not able to receive oral BRV for down titration, may receive iv BRV for down titration. In the latter circumstance, the subjects may receive more than 10 consecutive doses of iv BRV in accordance with the Investigator's discretion. A 2-week Safety (BRV-free)

Period will follow the final dose of BRV. In this SAP, the Down-Titration period is considered part of the Follow-Up period, which is described more in [Section 3.2.4](#).

Safety assessments will be collected throughout these periods.

## 2.4 Determination of sample size

The primary objective of the study is to evaluate the PK, safety, and tolerability of BRV given intravenously. The plan for approximately 50 enrolled subjects (4 age cohorts of approximately 12 subjects each) to receive iv BRV was deemed clinically appropriate for the evaluation of the PK, safety, and tolerability of iv BRV administration in subjects  $\geq 1$  month to  $< 16$  years of age with epilepsy. No formal sample size calculation has been performed.

## 3 DATA ANALYSIS CONSIDERATIONS

### 3.1 General presentation of summaries and analyses

Statistical analysis and generation of tables, figures, subject data listings, and statistical output will be carried out using SAS Version 9.3 or higher. All summaries will be descriptive; no statistical hypothesis testing is planned. All tables and listings will use Courier New font size 9.

Tables, figures and listings (TFL) will be displayed for the defined analysis sets. If the Safety Set (SS) and the Safety Set-iv (SS-iv) consist of the same number of subjects, TFLs will only be presented for the SS-iv.

For categorical parameters, the number and percentage of subjects in each category will be presented. The denominator for percentages will be based on the number of subjects appropriate for the purpose of the analysis. Unless otherwise noted, all percentages will be displayed to 1 decimal place. No percentage will be displayed for zero counts, and no decimal will be presented when the percentage is 100%.

For continuous parameters, descriptive statistics will include number of subjects (n), mean, standard deviation (SD), median, minimum, and maximum, unless otherwise stated.

Decimal places for descriptive statistics will always apply the following rules unless otherwise stated:

- “n” will be an integer
- Mean, SD, geometric mean, and median will use 1 additional decimal place compared to the original data
- CV [%] will be presented with 1 decimal place
- Minimum and maximum will have the same number of decimal places as the original value

However, the maximum number of decimals displayed will not exceed 4.

All summaries, unless otherwise stated, will be presented overall for all subjects, by age cohorts (Cohort 1:  $\geq 12$  to  $< 16$  years, Cohort 2:  $\geq 6$  years to  $< 12$  years, Cohort 3:  $\geq 2$  to  $< 6$  years, Cohort 4:  $\geq 1$  month to  $< 2$  years), and by infusion duration (15-minute iv infusion and iv bolus (up to 2-minute infusion)). Selected tables will be provided in addition by subject groups (OLB, RxB and IOB combined, and IIB), or by scheduled assessment timepoints as defined in [Section 4.8](#).

Selected summaries will be repeated by the country of enrollment (Hungary and rest of the World).

A complete set of listings containing all documented data and relevant derived data (eg, change from Baseline) will be generated. Summary tables will only contain data from subjects and visits which have been foreseen by the protocol, eg. in the event data will be captured after TC-1 when it is not required, this data will only be listed and not summarized.

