12.4.1 Analysis of safety variables

Descriptive statistics for the safety variables will be presented by cohort and infusion duration, cohorts overall, and all subjects overall. Additional summaries will include a summary of the OLB, RXB, IOB, and IIB groups by cohort and infusion duration.

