## 6 DEMOGRAPHICS AND OTHER BASELINE CHARACTERISTICS

### 6.1 Demographics and other Baseline Characteristics

Demographic variables will be presented for the SS-iv and the SS. The variables to be presented are:

- Age at entry into EP0065 (in years for subjects aged >2 years at study entry, in months for subjects aged ≤ 2 years at study entry)
- Age at first diagnosis (in years and in months) (as defined in [Section 3.2.7](#))

- Duration of epilepsy (in years and in months) (as defined in [Section 3.2.8](#) )
- Categorized age at entry into EP0065:
  - EudraCT age categories:  $\geq 1$  month to  $< 24$  months,  $\geq 24$  months to  $< 12$  years,  $\geq 12$  to  $< 16$  years
  - Age categories for submission:  $\geq 1$  month to  $< 4$  years,  $\geq 4$  to  $< 16$  years
- Gender (male, female)
- Subject group (OLB, RxB, IOB, and IIB)
- Weight at Screening (kg)
- Weight at baseline (kg)
- Weight group at baseline ( $< 50$  kg,  $\geq 50$  kg)
- Height at Screening (cm)
- BMI at Screening ( $\text{kg}/\text{m}^2$ ) (as defined in [Section 3.3](#))
- Racial group (American Indian/Alaskan Native, Asian, Black, Native Hawaiian or Other Pacific Islander, White, Other/Mixed)
- Ethnicity (Hispanic or Latino or Not Hispanic or Latino)
- Country (Countries may include Czech Republic, France, Germany, Hungary, Italy, Ireland, Mexico, Poland, Spain, USA)
- VNS Status (VNS not used, VNS used; if used: VNS active, VNS not active)

The following listings will be provided by age cohort for all subjects screened:

- demographics at Screening
- childbearing potential at Screening
- historical seizure count (describing the type and number of seizures experienced in the 3 weeks prior to Screening)
- diagnosis of epilepsy (describing the primary disease, date of first epilepsy diagnosis and history of status epilepticus prior to the 1-month period before Screening)
- vagus nerve stimulation status at Screening
- family medical history (family medical history is only collected for subjects with potential drug-induced liver injury and will describe the medical conditions including start and stop dates)
- lifestyle (lifestyle information is only collected for subjects with potential drug-induced liver injury and will describe the alcohol- and illicit drug use within past 6 months)

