## 9 PHARMACOKINETICS

### 9.1 Pharmacokinetics

Plasma concentration of BRV (parent compound only) before, during and after iv BRV administration will be summarized and listed for the PK-PPS.

Descriptive statistics will be calculated for each timepoint by infusion duration, visit and age cohort. These statistics will also be repeated by visit and weight group (<50 kg, ≥50 kg) and by visit and subject group (OLB, RxB and IOB combined, and IIB separately). Descriptive statistics will include: the number of observed values, geometric mean, 95% confidence interval for geometric mean, geometric CV, mean, SD, median, minimum value and maximum value. Values below LOQ will be set to LOQ for all calculations.

Box plots of plasma concentration of BRV at each timepoint (15 minutes and 3 hours) will be produced for each age cohort by visit. Infusion duration will be marked using different symbols.

Box plots of plasma concentration of BRV at each timepoint (15 minutes and 3 hours) will be produced for each infusion duration by visit. Age groups will be marked using different symbols.

A listing for plasma sample collection times and concentrations of BRV will be provided.

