### 10.2.1 AE summaries

All AE tables will be summarized separately over all AEs and by MedDRA SOC and MedDRA PT. The number and percentage of subjects experiencing each event at least once will be summarized. All summaries will be sorted alphabetically by SOC and by frequency of events within PTs, starting with the most frequent event overall. All summaries are for all study periods combined (Screening, IOB treatment, iv-PK, Follow-up, and Safety (BRV free) Period) unless otherwise indicated. Only the first occurrence of a TEAE of a particular PT will be included in incidence calculations, but all occurrences of TEAEs of the same PT will be included in counts of TEAEs. For summaries by study period, AEs are assigned only to the period on which they began. TEAEs of interest is a selection of TEAEs identified by UCB to be of interest to BRV.

The following summaries will be produced overall and by age cohort, for all subjects and separately by infusion duration, and subject group for the SS-iv:

- Incidence of AEs – Overview (number and percentage of subjects with at least one: AE, TEAE, serious TEAE, non-serious TEAE, TEAE of interest, TEAE requiring dose change,

drug-related TEAE, drug-related serious TEAE, and severe TEAE, as well as the number and percentage of subjects who discontinued due to a TEAE, had permanent withdrawal of BRV due to a TEAE, had an AE leading to death, and had a TEAE leading to death)

- Incidence of TEAEs
- Incidence of TEAEs Leading to Study Discontinuation
- Incidence of Serious TEAEs

The following AE summaries will be produced overall and by age cohort, for all subjects and separately by infusion duration for the SS-iv:

- Incidence of PTAEs
- Incidence of TEAEs by Maximum Intensity  
Each subject will be counted at most once per primary SOC or PT according to the maximum intensity of all AEs within that SOC or PT. Severe intensity will be assumed for AEs for which intensity is not specified.
- Incidence of TEAEs by Maximum Relationship  
Drug-related AEs are AEs for which the relationship to trial medication is specified as related or AEs for which relationship is not specified.
- Incidence of TEAEs of Interest
- Incidence of Non-serious TEAEs Occurring in at least 5% of Subjects
- Incidence of Serious TEAEs by Relationship to BRV
- Incidence of Fatal TEAEs by Relationship to BRV

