The following summaries will also be produced by country of enrollment (Hungary and rest of the World) for all subjects, by infusion duration and by subject group for the SS-iv:

- Incidence of AEs – Overview
- Incidence of TEAEs

The following summary will also be produced by country of enrollment (Hungary and rest of the World) for all subjects and by infusion duration for the SS-iv:

- Incidence of TEAEs by Maximum Intensity

The following summaries will be produced overall and by age cohort and study period, for all subjects and separately by infusion duration and subject group for the SS:

- Incidence of TEAEs by Study Period
- Incidence of TEAEs Leading to Study Discontinuation by Study Period
- Incidence of Serious TEAEs by Study Period

The following summaries will be produced overall and by age cohort and study period, for all subjects and by infusion duration for the SS:

- Incidence of TEAEs by Maximum Intensity by Study Period

- Incidence of TEAEs by Maximum Relationship by Study Period

The following TEAE summaries will be produced overall and by age cohort for the SS:

- Incidence of Serious TEAEs - Subject Numbers
- Incidence of TEAEs Leading to Study Discontinuation - Subject Numbers

Additionally, incidence of TEAEs will be summarized by categorized relative time infusion for all subjects, and by age cohort for the SS-iv. The time of each AE relative to the start of the previous iv infusion will be calculated as described in [Section 3.2.4](#) and categorized into 0- $\leq$ 5 minutes,  $>5 - \leq 15$  minutes,  $>15$  to  $\leq 60$  minutes,  $>60 - \leq 12$  hours and  $>12$  hours.

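### The protocol promises a four-group safety summary, but the SAP's subject groups merge IOB with OLB and RxB and SAP 3.10 does not declare the change

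*SAP*

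**What the plan says.** Protocol 12.4.1, on the safety variables, states: "Additional summaries will include a summary of the OLB, RXB, IOB, and IIB groups by cohort and infusion duration".

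SAP 3.1 sets the general rule for tables: "Selected tables will be provided in addition by subject groups (OLB, RxB and IOB combined, and IIB". SAP 9.1 repeats it for the PK summaries: "by visit and subject group (OLB, RxB and IOB combined, and IIB separately". The demographics list in SAP 6.1 keeps all four levels: "Subject group (OLB, RxB, IOB, and IIB".

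SAP 10.2.1 produces the AE overview, TEAEs, TEAEs leading to study discontinuation and serious TEAEs "for all subjects and separately by infusion duration, and subject group for the SS-iv", and adds that, unless otherwise indicated, "All summaries are for all study periods combined". TEAEs, discontinuation TEAEs and serious TEAEs are then repeated "by age cohort and study period, for all subjects and separately by infusion duration and subject group for the SS". SAP 10.5.1 and 10.5.2 give observed values and changes from baseline by subject group or subgroup. None of these sections names the levels.

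SAP 2.3 describes the group at issue: "Initiating Oral BRV (IOB) subjects: not currently receiving BRV; first dose of BRV in EP0065 will be oral tablet or solution".

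**The concern.** AEs and withdrawals due to AEs are the primary safety variables, and tolerability is part of the primary objective. The protocol names the four entry groups separately for the safety summaries. A SAP followed as written would leave that summary out and would not say so.

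The merged column is mixed in ways that bear on safety. IOB children are not on brivaracetam at entry and may reach the first infusion after as little as 2 days of oral drug. OLB and RxB children are already taking it. The period in which an AE counts as treatment-emergent also differs, as does the maximum dose. A reader of the main AE tables could not tell whether events around the infusion came from children who had just started the drug or from those already on it. The mix of groups is also not fixed by design: there is no randomization, infusion modes fill in sequence, and neither document sets a quota by entry group.

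**Working it through.** **1. How many groups SAP 3.1 defines.** Its wording could be read as three groups, with OLB standing alone. SAP 9.1 uses the same phrase and sets IIB apart, and the version 4.0 change entry in SAP 13.3 describes the first three as a combination. The reading is therefore two groups: OLB+RxB+IOB, and IIB.

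**2. Protocol and SAP side by side.**

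| Place | Levels of subject group |
|---|---|
| Protocol 12.4.1 (safety) | OLB, RxB, IOB, IIB |
| SAP 3.1 (general rule) | OLB+RxB+IOB; IIB |
| SAP 6.1 (demographics) | OLB, RxB, IOB, IIB |
| SAP 9.1 (PK) | OLB+RxB+IOB; IIB |
| SAP 10.2.1, 10.5.1, 10.5.2 (safety) | not stated; 3.1 applies by default |
| SAP 3.10 (declared changes) | subject groups not mentioned |

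SAP 3.10 declares changes to the PK per-protocol set and to the infusion epochs. SAP 13.3 records the combination only under Section 9.1, which is PK.

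**3. What the merged column combines.**
- *Counting window (SAP 10.2).* Every AE is treatment-emergent for OLB and RxB. For IOB, only AEs from the IOB Treatment Period onward are. SAP 10.5.1 and 10.5.2 apply the same rule to treatment-emergent possibly clinically significant (PCST) vital-sign and ECG values.
- *Maximum dose (SAP 2.3).* 5 mg/kg/day (rounded) for OLB and RxB, 4 mg/kg/day for IOB.
- *Periods (SAP 10.2.1).* The main AE tables pool all periods, so IOB events during oral initiation share a column with OLB and RxB events during Screening.

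**4. What remains visible.** IIB has its own column. Only IOB children may enter the IOB Treatment Period, so the by-period tables isolate AEs that start there. They do not separate IOB from OLB and RxB in the iv PK or Follow-up Periods. The vital-sign and ECG PCST percentage tables have no subject-group split at all.

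**5. Size of the effect.** Let s be the IOB share of the merged group, p_I the IOB rate and p_E the OLB/RxB rate.

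Merged rate = s·p_I + (1−s)·p_E, so merged rate − p_E = s·(p_I − p_E).

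The column shows a fraction s of any IOB difference, whatever the rates. The documents give neither s nor the rates. Over assumed shares of 10%, 25%, 50% and 75%, the column would show 10%, 25%, 50% and 75% of whatever difference exists, including none.

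**6. Cell sizes.** The plan's own figure is about 50 subjects: 4 cohorts × 12 = 48, which agrees. Average cell sizes at 50, assuming an even spread:
- four groups × 4 cohorts × 2 durations = 32 cells; 50/32 = 1.6
- two groups × 4 cohorts × 2 durations = 16 cells; 50/16 = 3.1
- four groups × 2 durations = 8 cells; 50/8 = 6.3

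**The case against.** The pooling follows the design. At the first infusion OLB, RxB and IOB children share one rule, a milligram-for-milligram switch from the oral dose, and IOB children must have had no dose change for 2 days. IIB children alone begin with an infusion. Oral-to-iv switch against iv initiation is a sensible contrast for infusion-related AEs, vital signs and ECGs as well as for PK. This stands, and is why the two-group split should be kept.

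The information is also not lost. All AEs are listed, vital signs and ECGs are plotted by subject, vital-sign PCST occurrences are tabulated by subject with subject group shown, and demographics disclose the four-group mix. This stands in part: listings allow reconstruction, but they are not the summary the protocol promises.

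Sparse cells are a fair reason for restraint. The two-group version averages only 3.1 per cell when fully crossed, however, so sparsity does not explain the merge.

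A reader might infer that tolerability in new starters generally is diluted. The documents do not support that, because IIB stays separate and IOB oral-initiation AEs are isolated by period. A reader might also infer that OLB and RxB children are proven tolerators. The documents say only that they are currently receiving the drug. Inclusion criterion 7 asks for a regimen unchanged for 7 days before Screening, and no minimum time on brivaracetam is set, while IOB children may have up to 10 days of oral treatment.

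**Conclusion.** The point holds as an undeclared departure from a protocol-defined safety summary, together with an inconsistent definition of subject group within the SAP. Its consequence is limited but real. In the main SS-iv AE tables, and in iv PK and Follow-up Period safety summaries, IOB children cannot be separated from children on brivaracetam at entry, although counting windows and dose ceilings differ.

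No bias of known size follows. Group sizes and event rates are not in the documents, and all analyses are descriptive. Four columns would not make the infusion modes comparable either, since mode is assigned in sequence.

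The conclusion rests on SAP 3.1 governing Sections 10.2 and 10.5 by default. A programmer who took the levels from SAP 6.1 would produce four groups, which is itself a reason to settle the definition. A reader might also infer that every safety table must carry four groups. Protocol 12.4.1 does not say so; it promises a summary.

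**What to change.** - Define subject group once in SAP 3.1, with its levels, and have Sections 6.1, 9.1, 10.2 and 10.5 refer to it.
- Keep the two-group split for PK and for the contrast of oral-to-iv switch against iv initiation.
- Add a four-group display (OLB, RxB, IOB, IIB), by infusion duration and by cohort, as descriptive counts. Provide it at least for the AE overview, TEAEs, TEAEs leading to discontinuation, and the vital-sign and ECG PCST summaries.
- Record any remaining merge, with its reason, in SAP 3.10.
- Do not pool IOB with IIB as a way round small cells. That would hide the iv starters the SAP now shows and would mix two different treatment-emergent windows.

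The cost is SAP wording and extra table columns. Group membership is already needed for SAP 6.1, and no data collection or study procedure changes. The drawback is sparse cells: about 1.6 children on average if fully crossed, about 6.3 if shown by infusion duration alone. The figures should be read as counts.
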